Cover Page

Title: Artificial Intelligence Screening for Body Dysmorphic Disorder in Aesthetic Surgery: Improving Patient Safety and Outcomes

• NCT Number: [NCT Number Here]

• **Document Date:** August 30, 2024

• **Document Review Statement:** This document was most recently updated and reviewed by the sole researcher, [name], EMBA, on August 30, 2024. As there is no human subjects protection review board required for this study, this date reflects the most recent review and update by the principal investigator.

Study Protocol

Introduction: This study protocol outlines the procedures, objectives, and methodologies for the observational study titled "Artificial Intelligence Screening for Body Dysmorphic Disorder in Aesthetic Surgery: Improving Patient Safety and Outcomes." The primary aim is to evaluate the clinical utility of an Al-powered screening tool for Body Dysmorphic Disorder (BDD) in patients seeking elective aesthetic surgery.

Study Objectives

- To evaluate the effectiveness of the Al-based screening tool in identifying patients at risk for BDD.
- To determine the correlation between various demographic and psychological factors (such as age, gender, and stress levels) and positive BDD screening results.
- To assess the impact of early psychological intervention on surgical decision-making and outcomes.

Study Design

This is an observational study with a prospective time perspective. The study involves the collection of clinical and psychological data from patients seeking elective aesthetic surgery. The AI model analyzes this data to provide risk scores and identify patients who may benefit from psychological intervention.

Participant Eligibility

Inclusion Criteria:

- Individuals aged 18 and older.
- Completion of the Body Dysmorphic Disorder Questionnaire (BDDQ).

Exclusion Criteria:

- Individuals below 18 years of age.
- Patients who did not complete the Body Dysmorphic Disorder Questionnaire (BDDQ).

Study Population Description

Participants are individuals seeking elective aesthetic surgery. They will complete the BDDQ and provide demographic and psychological data, including age, gender, and recent stress levels. The AI model will analyze this information to screen for BDD.

Data Collection: The following data will be collected from each participant:

- Age
- Gender
- Stress levels
- BDDQ scores
- Surgical outcomes (where applicable)
- Patient satisfaction (as measured by the Visual Analog Scale, VAS)

Study Procedures

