Participants will undergo a screening assessment using the Al model, which evaluates multiple factors based on their responses to the BDDQ and additional psychological data. The Al model will generate risk scores and recommendations for psychological referral if necessary.

Follow-Up

The follow-up period for this study ranges from 1 to 43 months post-surgery, with a mean follow-up of 22 months. Data on patient satisfaction and surgical outcomes will be collected and analyzed.

Outcome Measures

Primary Outcome Measure

- Title: Patient Satisfaction Post-Surgery
- **Description:** The primary outcome measure is the level of patient satisfaction with the cosmetic surgery results, measured using the Visual Analog Scale (VAS) within the follow-up period after surgery.

Secondary Outcome Measure

- Title: Correlation Between Positive BDD Screening and Risk Factors
- Description: This measure evaluates the correlation between a positive Body Dysmorphic Disorder (BDD) screening result and various risk factors, including demographic factors (age, gender), psychological stress levels, and previous psychiatric history. The study will utilize chi-square tests to analyze gender differences in the prevalence of BDD among the patient population.

The goal is to identify patterns that could inform better patient selection and management in cosmetic surgery.

Conclusion

This study protocol provides a comprehensive overview of the study design, objectives, data collection methods, and outcome measures for the observational study "Artificial Intelligence Screening for Body Dysmorphic Disorder in Aesthetic Surgery: Improving Patient Safety and Outcomes." The integration of Al-powered screening is expected to improve patient selection, surgical planning, and overall outcomes in aesthetic surgery.

Statistical Analysis Plan (SAP)

Introduction: This Statistical Analysis Plan (SAP) outlines the statistical methods and analyses to be performed for the study titled "Artificial Intelligence Screening for Body Dysmorphic Disorder in Aesthetic Surgery: Improving Patient Safety and Outcomes." The primary aim of the study is to assess the effectiveness of the Al-powered screening tool in identifying patients at risk for BDD and its impact on surgical decision-making.

Study Objectives:

- To evaluate the effectiveness of the Al-based screening tool in identifying patients at risk for BDD.

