# Calculate the relative risk
relative_risk = (positive_BDD_male / positive_BDD_female) /
(negative_BDD_male / negative_BDD_female)
```

Outcome Analysis:

 Patient satisfaction levels as measured by the Visual Analog Scale (VAS).

Data Analysis:

Data analysis will be performed using Python in a Colab environment.
 The analysis will focus on correlations between BDD and identified risk factors, chi-square tests for gender differences, as well as the effectiveness of the AI model in screening for BDD.

Access Instructions: To request permission to access the individual participant data (IPD) and supporting information, please email [contact]. Detailed instructions for requesting access can be found at IPD Sharing Instructions.

Conclusion: This SAP provides a detailed plan for the statistical analysis of the study "Artificial Intelligence Screening for Body Dysmorphic Disorder in Aesthetic Surgery: Improving Patient Safety and Outcomes." The analysis aims to provide insights into the effectiveness of the AI model in identifying and managing patients at risk for BDD, ultimately improving surgical outcomes and patient safety.

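### The SAP's primary aim, AI effectiveness and impact on surgical decisions, has no specified analysis with a comparator, performance metric or surgical-decision variable

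*Combined protocol and SAP*

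**What the plan says.** The SAP Introduction sets the goal: "The primary aim of the study is to assess the effectiveness of the" AI-powered "screening tool in identifying patients at risk for BDD and its impact on surgical decision-making". The protocol Introduction words its own primary aim differently, as the tool's clinical utility. Both Study Objectives lists put AI effectiveness first. Third in each is the effect of early psychological intervention on surgical decisions and outcomes.

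The SAP's Data Analysis section returns to the theme: "The analysis will focus on correlations between BDD and identified risk factors, chi-square tests for gender differences, as well as the effectiveness of the". That sentence goes on to name the screening model as its subject. The SAP Conclusion hopes for insight into how the model performs "in identifying and managing patients at risk for BDD, ultimately improving surgical outcomes and patient safety".

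On the tool itself, the protocol's Study Procedures describe an assessment "which evaluates multiple factors based on their responses to the BDDQ and additional psychological data", and add that the "model will generate risk scores and recommendations for psychological referral if necessary". Of participants, the Study Population Description says: "They will complete the BDDQ and provide demographic and psychological data, including age, gender, and recent stress levels". The AI then analyses this information.

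The protocol's primary outcome is VAS satisfaction after surgery. Its secondary outcome is the "correlation between a positive Body Dysmorphic Disorder (BDD) screening result and various risk factors". The Follow-Up section says that surgical outcome data will be gathered and analysed.

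**The concern.** A primary aim needs at least one planned analysis whose result could answer it. An aim about identifying at-risk patients needs the tool's output, something to compare it with, and a measure of how well the two correspond. An aim about surgical decisions needs a record of those decisions and a comparison. The SAP states both aims but attaches none of these elements to either.

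Any later statement that the tool identifies at-risk patients, or changes who is operated on, would therefore rest on an analysis nobody had planned. The title and both conclusions concern patient safety and outcomes, so an unsupported claim could mislead readers who are considering the tool for patient selection. Readers also could not tell whether the reported risk factors describe people with a positive questionnaire or the model's use of its own inputs.

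**Working it through.** No arithmetic applies. The documents give no sample size, error rate, effect size or accuracy target. The check is to list every analysis in the SAP and look in each for what the primary aim requires.

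| SAP analysis | Variables named | Comparator for the AI | Performance metric | Surgical decision |
|---|---|---|---|---|
| Descriptive statistics | positive screens, demographics, stress | none | none | none |
| Pearson correlations (four) | `BDD` with age, stress, male, female | none | none | none |
| Chi-square test | `BDD` by gender | none | none | none |
| Sex ratios and the quotient labelled relative risk | `BDD`, male, female | none | none | none |
| Outcome Analysis | VAS satisfaction, no method | none | none | none |
| Data Analysis sentence | AI effectiveness, as a focus only | none | none | none |

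The code uses five columns: `BDD`, age, stress over the last three months, male and female. Whether an AI output is among them depends on what `BDD` is. The code shows only 0/1 coding. The secondary outcome speaks of a positive screening result, while the chi-square section speaks of prevalence. Neither names the instrument or the cut-off. There are three possibilities:

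1. **`BDD` is the BDDQ result.** No AI output enters any specified analysis, so nothing about the AI can be concluded.
2. **`BDD` is the AI flag.** An AI output is analysed, but only against age, gender and stress. These associations do not show whether the flagged patients are those at risk. Age, gender and stress are also among the data the model analyses, so part of any correlation may come from how the model is built.
3. **`BDD` is something else, such as a clinical diagnosis.** The AI again enters no analysis, and no such measure appears in the data collection lists.

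The identification half of the aim is unanswered in all three cases.

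Could the BDDQ serve as comparator? It is the only BDD measure listed, but its responses feed the model. Agreement between the AI flag and the BDDQ would partly be agreement of an output with its own input, and so not independent evidence of accuracy.

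For the surgical-decision half, the nearest item is surgical outcomes, listed under Data Collection with a qualifier that they may not apply to everyone. They may imply who was operated on, but they do not record the decision, and the SAP gives no method for them. The third objective has the same gap: neither referral nor psychological intervention appears in the data lists or the analyses.

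VAS satisfaction does not fill either gap. It measures how operated patients feel about the result, and no analysis links it to the AI.

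**The case against.** The best defence is that the SAP does mention AI effectiveness in Data Analysis, and that `BDD` may itself be the AI's output, since the protocol describes the AI as doing the screening. On that reading the frequency, correlation and chi-square analyses all use an AI result. This stands in part. A reader might infer that the AI is absent from every analysis, and the documents do not support that. They leave the source of `BDD` open. The Data Analysis sentence, however, states an intention without a variable, comparator or metric, and the AI-flag reading still leaves the aim untested.

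Other stronger readings also fail:

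- *AI scores are not kept.* The data collection lists omit them, but they also omit previous psychiatric history, which the secondary outcome uses. The lists are not exhaustive, so their silence proves nothing about storage.
- *Surgical outcomes will not be analysed.* The protocol's Follow-Up section says they will be. What is missing is a method in the SAP.
- *The SAP commits to showing better outcomes.* Its Conclusion states an aim of providing insight, with improvement as a hoped-for consequence.

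**Conclusion.** The point holds. The SAP's primary aim has no specified analysis able to answer it: of the six entries tabulated, none supplies a comparator, a performance metric or a surgical-decision variable. This is more than missing detail, because carrying out the plan exactly leaves the central question unanswered under every reading of `BDD`. It should be settled before results are reported.

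The size is qualitative. A reader might infer that the tool is inaccurate, or that agreement with the BDDQ would inflate its apparent accuracy. The documents support neither. They give no model weights, BDDQ accuracy or stress relation from which a direction or amount could be derived. The conclusion assumes only that the SAP's list of analyses is complete as written.

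**What to change.** 1. State the source and cut-off of `BDD`. If it is the AI flag, label its associations with age, gender and stress as those of an output with its own inputs. The choice of source can stay with the sponsor.
2. Retain as study data, where available, the AI score, flag and referral recommendation that the tool already generates, and whether surgery was performed.
3. Cross-tabulate the AI flag against the BDDQ result, and against surgery performed, with 95% confidence intervals. Report these as agreement and association, not as accuracy or effect.
4. Restate every effectiveness or impact statement to match: the primary aims in both Introductions, the first and third objectives in both the protocol and the SAP, the Data Analysis focus, and both Conclusions.

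An independent reference standard for BDD is needed only if the sponsor keeps the effectiveness claim. It would require extra assessments and is not part of this fix.

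The cost is wording, one variable definition, retention of existing outputs and operated status, and two cross-tabulations. The downside is a more modest claim. The precision of the tables cannot be judged without a sample size. The protocol gives follow-up of 1 to 43 months with a mean of 22, which reads as if data may already exist, although the documents do not settle this. If they do exist, AI outputs may not be retrievable for every patient. The restatement in item 4 is still possible then.

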# Correlation calculations
stats.pearsonr(corr4['BDD'], corr4['Age'])
stats.pearsonr(corr4['BDD'], corr4['Stress in the last 3
months'])
stats.pearsonr(corr4['BDD'], corr4['Male'])
stats.pearsonr(corr4['BDD'], corr4['Female'])
```

• Chi-Square Analysis:

 Chi-square tests will be conducted to evaluate the differences in the prevalence of BDD between genders, helping to identify any statistically significant associations between gender and BDD.

Python code

```
from scipy.stats import chi2_contingency

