- To determine the correlation between various demographic and psychological factors (such as age, gender, and stress levels) and positive BDD screening results.
- To assess the impact of early psychological intervention on surgical decision-making and outcomes.

Study Design: This is an observational study with a prospective time perspective. The study involves the collection of psychological and demographic data from patients seeking elective aesthetic surgery. The Al model analyzes this data to identify at-risk patients and provide recommendations for psychological evaluation.

Data Collection: The following data will be collected from each participant:

- Age
- Gender
- Stress levels
- BDDQ scores
- Surgical outcomes (where applicable)
- Patient satisfaction (as measured by the Visual Analog Scale, VAS)

Statistical Methods:

• Descriptive Statistics:

- Frequency and percentage of patients screening positive for BDD.
- Analysis of demographic data and stress factors.

Pearson Correlation:

o Correlation between BDD and factors such as age, gender, and stress.

Python code

```

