# Create a contingency table
                        pd.crosstab(tabla1['BDD'],
contingency_table
tabla1['Female'])

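### The gender analysis is stated as a comparison of BDD prevalence, but the study observes only a screening result, and the analysed `BDD` column is not defined

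*Combined protocol and SAP*

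**What the plan says.** Two places state the gender comparison in terms of the disorder. The SAP, under Chi-Square Analysis, will "evaluate the differences in the prevalence of BDD between genders". The protocol, under Secondary Outcome Measure, plans "chi-square tests to analyze gender differences in the prevalence of BDD among the patient population".

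Other places describe a screening result. The same secondary outcome opens as a "correlation between a positive Body Dysmorphic Disorder (BDD) screening result and various risk factors", and the SAP's Descriptive Statistics will give "Frequency and percentage of patients screening positive for BDD".

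The Data Collection lists in both documents hold age, gender, stress, BDDQ scores, surgical outcomes and VAS satisfaction. The protocol's Study Population Description says that participants complete the BDDQ and "provide demographic and psychological data, including age, gender, and recent stress levels", and that the AI "model will analyze this information to screen for BDD".

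The code cross-tabulates a column named `BDD` (the call begins "pd.crosstab(tabla1['BDD") with gender. It then computes a statistic beginning "relative_risk = (positive_BDD_male / positive_BDD_female", divided by the same male-to-female ratio among the negatives. The Pearson correlations with age, stress and gender also use a column named `BDD`. No text says how that column is built.

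**The concern.** A comparison of prevalence needs disorder status, and the listed data contain none. A psychological evaluation may follow an AI recommendation, but its result is not among the data to be collected. Previous psychiatric history is named as a risk factor; it is not a BDD diagnosis and is also absent from the lists.

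The undefined column leaves two readings, and neither supports the stated claim:

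- **`BDD` is BDDQ-positive.** The test is then clear, but its result concerns questionnaire positivity, which mixes true cases with false positives and omits missed cases.
- **`BDD` is the AI flag.** Gender, age and stress are then on both sides of the test. An association may reflect how the model weights its inputs and could appear without any difference in the disorder.

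The protocol wants these patterns to inform patient selection and management. A gender difference reported as disorder prevalence could be used in that way when it reflects screening error or model weighting.

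**Working it through.** The documents state no prevalence, gender ratio, sensitivity or specificity, so there is no planned figure to reproduce. All values of sensitivity (Se), specificity (Sp) and true prevalence (p) below are assumptions, chosen to show the range of behaviour.

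**1. Screen-positive proportion against true prevalence**

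Screen-positive proportion = Se × p + (1 − Sp) × (1 − p). It exceeds p only when p < (1 − Sp) / [(1 − Se) + (1 − Sp)].

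| Se | Sp | Screen-positive at p = 10% | Overstated only if p is below |
|---|---|---|---|
| 0.90 | 0.90 | 0.090 + 0.090 = 18.0% | 0.10/0.20 = 50% |
| 0.90 | 0.80 | 0.090 + 0.180 = 27.0% | 0.20/0.30 = 67% |
| 0.80 | 0.99 | 0.080 + 0.009 = 8.9% | 0.01/0.21 = 4.8% |
| 0.80 | 1.00 | 0.080 + 0 = 8.0% | 0% |

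The same true 10% can therefore be over- or understated.

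**2. What the SAP's ratio is**

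The code computes (male positives / female positives) / (male negatives / female negatives), which is the male-to-female odds ratio. With 15 of 100 men and 10 of 100 women positive it gives (15/10) / (85/90) = 1.59. The ratio of proportions is 0.15/0.10 = 1.50.

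**3. Effect of screening error on the gender comparison**

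The formula in step 1 is applied to each gender. The ratio is men to women.

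| True women / men | Se (both) | Sp women / men | Screen-positive women / men | Ratio of proportions | SAP formula |
|---|---|---|---|---|---|
| 10% / 15% | no error | no error | 10% / 15% | 1.50 | 1.59 |
| 10% / 15% | 0.90 | 0.90 / 0.90 | 18.0% / 22.0% | 1.22 | 1.28 |
| 10% / 15% | 0.90 | 0.80 / 0.80 | 27.0% / 30.5% | 1.13 | 1.19 |
| 10% / 15% | 0.80 | 1.00 / 1.00 | 8.0% / 12.0% | 1.50 | 1.57 |
| 10% / 15% | 0.90 | 0.90 / 0.80 | 18.0% / 30.5% | 1.69 | 2.00 |
| 10% / 15% | 0.90 | 0.80 / 0.90 | 27.0% / 22.0% | 0.81 | 0.76 |
| 10% / 10% | 0.90 | 0.90 / 0.80 | 18.0% / 27.0% | 1.50 | 1.68 |

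With equal error in both genders the ratio shrinks toward 1, or stays at 1.50 when specificity is perfect. With unequal error it can grow, reverse, or appear where there is no true difference.

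**The case against.** The strongest reply is that the prevalence wording is shorthand. The objective, the title of the secondary outcome, its opening sentence and the descriptive analysis all speak of positive screening, and the only frequency the SAP promises is of screen-positives. This has weight: most of the plan is already worded correctly, and the documents draw no conclusion about how common the disorder is. But the gender test is the one inferential comparison described in words in both documents, and both describe it as prevalence, with no caveat and no column definition to settle the meaning.

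A second reply is that, if the screen errs equally in men and women, no true difference implies no screen-positive difference, so the chi-square null is preserved and only magnitude and power suffer. That is correct under its condition. The documents do not establish the condition, and it is doubtful for an AI flag whose inputs include gender.

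A third reply is that the choice of analysed column belongs to the sponsor. Defining it is the necessary part. The BDDQ result is recommended for the risk-factor tests because the documents list it separately from age, gender and stress, which avoids the overlap between outcome and inputs.

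A reader might also go further and infer that prevalence is probably overstated and the gender ratio pulled toward 1. The documents support neither direction. Overstatement reverses for a very specific but less sensitive screen, and shrinkage toward 1 can be relied on only with equal error in both genders and imperfect specificity.

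**Conclusion.** The point stands as an error of labelling and definition in a secondary outcome; the primary outcome, VAS satisfaction, is unaffected. As written, the plan would report a gender difference in a quantity it does not observe, and it may test a model's output against that model's inputs.

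Relabelling changes no computed number; it changes what may be concluded. The size and direction of bias in the rate and in the ratio are unknown. The 8.0% to 27.0% spread around a true 10%, and the apparent ratios of 0.81 to 1.69 for a true 1.50, rest entirely on assumed accuracy and show only that no direction can be presumed.

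The AI-flag problem depends on the column being that flag, which the documents leave open. They place gender among the data the model analyses but do not say how much weight it receives, so an association produced by the model is possible, not shown.

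**What to change.** 1. In the protocol's Secondary Outcome Measure and the SAP's Chi-Square Analysis, replace the reference to prevalence of the disorder with the proportion screening positive. Use the same term for the Pearson correlations.
2. Define the analysed column. Use the BDDQ result, with its positivity rule stated, for the risk-factor tests. Hold the AI flag in a separate, separately named column.
3. State that associations between the AI flag and its own inputs (gender, age, stress) will not be interpreted as risk factors.
4. Report the gender comparison as a ratio of screen-positive proportions with a 95% CI, in place of the odds ratio now labelled relative risk.
5. If a sensitivity table is added, let sensitivity and specificity differ by gender, and label the values as assumptions unless sourced. For each gender, corrected prevalence = [screen-positive proportion − (1 − Sp)] / (Se + Sp − 1). A correction with common error would hide the cases in which the ratio reverses.

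The cost is a few changes of wording, one column definition, a few lines of code and, optionally, a short table. No new data are needed. The downside is a more modest claim: the study would describe who screens positive, not who has the disorder.
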